7.1 Description of the research intervention

- (1) Interventions in the experimental group: standard antiparkinsonian therapy + stellate ganglion block.
- (2) Control group intervention: standard antiparkinsonian therapy.

7.2 Dosage and start and end times

Test group: Oral standard anti-Parkinsonian drugs, including compound levodopa, pramipexole hydrochloride, ropinirole, entacapone, amantadine, antan, etc. A total of three cycles of stellate ganglion block were performed, with 10 stellate ganglion blocks per cycle (once a day), with a 20-day interval between the two cycles;

Control group: Oral standard antiparkinsonian drug

8. Research Process

8.1 Screening Phase (Vs, -1 Day)

During the screening visit, the following procedures will be performed/collected:

Informed consent: After introducing the study to the subjects in detail and answering the subjects' doubts, the informed consent form signed by the patients was obtained. Sign up for pre-informed laboratory tests and imaging evaluations for routine clinical care, if relevant data are available within the specified window period. (If the subjects or their guardians cannot sign the informed consent form before the trial in the event of an emergency in the project, it needs to be clearly explained here) After the informed consent, the following procedures can be carried out.

Demographics: gender, date of birth, race, education, marriage, occupational information;

Relevant medication/surgery history;

vital signs: blood pressure, pulse rate, respiration and temperature;

Physical Exam: Internal Medicine and Neurology Physical Exam;

Laboratory tests: blood routine, serum biochemistry, coagulation, ceruloplasmin, gene expression level;

Previous/concomitant medications;

Blood biomarkers: IL-2, APEO, α -synuclein, DJ-1 protein, etc.;

Imaging examination: head MRI + susceptibility-weighted imaging;

Madopa equivalent dose;

Modified MDS-UPDRS scale;

NMSS scale;

PDQ-39 scale;

H&Y;

LDE;

10M-WT;

8.2 Randomization phase (V₁, 0 Day)

Randomize the eligible patients by stratified randomization method;

8.3 Follow-up period

Treatment stage: V2 4 weeks, V3 8 weeks, V4 12 weeks

During each treatment visit, the following procedures will be performed or the following metrics will be collected:

Detailed description: The following examinations need to be completed: vital signs; physical examination; laboratory examination; blood biomarkers: IL-2, APEO, α -synuclein, DJ-1 protein, etc.; imaging examination: head MRI + Susceptibility-weighted imaging (V4 only), etc.; Madopa equivalent dose; Modified MDS-UPDRS scale score; NMSS scale; PDQ-39 scale; H&Y classification; LDE; 10M-WT.

9. Subject withdraws from study or discontinues study treatment

9.1 Withdrawal Criteria

Reasons for a subject to withdraw from the study may include:

Subjects should withdraw from the trial when they have abnormal vital organ function, allergic reactions to drugs, poor compliance, exacerbation of disease or serious adverse reactions that require stopping the treatment of the trial drug or using other treatment methods;

Subjects who are ineffective, cannot tolerate adverse reactions, wish to take other treatment methods, or request to withdraw from the trial without any reason.

Subject withdrew informed consent and refused further follow-up;

Subjects lost to follow-up;

Subject died.

9.2 Criteria for discontinuation of study treatment

Criteria for subjects to discontinue study treatment are as follows:

(1) Subjects withdrew their informed consent for any reason or no reason and refused to continue receiving study drug treatment;

(2) According to the judgment of the investigator, the subject's clinical symptoms have deteriorated/physical condition has decreased, the study endpoint has been reached, or there are intolerable side effects, including any abnormal clinical or laboratory tests or other medical conditions;

(3) Other circumstances that the investigator deems necessary to terminate the study drug treatment;

(4) The sponsor terminated the study.

9.3 Steps to withdraw from the study or discontinue study treatment

Subjects must be checked for efficacy and safety in accordance with the protocol for withdrawal from the study and final observation and follow-up, and AEs and outcomes must be fully recorded. The researcher can suggest or provide alternative treatment methods to the subjects according to the actual situation of the subjects.

If the subject refuses to come to the research center for further visits, their survival status should continue to be tracked unless the subject withdraws informed consent. In this case, no further study evaluations should be conducted and no further data should be collected.

10. Evaluation indicators

10.1 Primary endpoint: Modified MDS-UPDRS scale score (the revised version of the Movement Disorders Association Unified Parkinson's Disease Rating Scale, which has four main parts, including both physician and patient aspects, the first part is psychological, behavioral and emotional; the second Part is activities of daily living; the third part is motor symptoms; the fourth part is complications), SGB is carried out in three cycles, each cycle is carried out for 6-10 days, and the interval between each cycle is 20 ± 7 days; The first, second, and third cycles of Day0, Day5, and the last day were measured and recorded.

10.2 Secondary endpoints : NMSS (Non-motor Symptom Evaluation Scale), PDQ-39 (Self-rating scale for clinical evaluation of the quality of life in patients with Kinson's disease), H&Y classification (Classification of Parkinson's disease), LDE (levodopa equivalent dose), 10M-WT (10m walk test), cerebrospinal fluid and blood biomarkers, SGB were carried out for a total of three cycles, each cycle was carried out for 6-10 days, and the interval between each cycle was 20 ± 7 days; On Day0, Day5, and the last day of the third cycle, the scale data were measured and recorded. The researchers performed head MRI + susceptibility-weighted imaging on Day 0 of the first cycle and Day 10 of the third cycle, respectively, to compare the changes in the "swallowtail sign" of two successive head MRIs.

11. Adverse events, serious adverse events, adverse reactions

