Title	Stellate Ganglion Block in Patients With Advanced Primary Parkinson' s Disease: a Small, Open, Randomized, Controlled Clinical Study
Bidders	Zhujiang Hospital of Southern Medical University
Leader of the unit	Zhujiang Hospital of Southern Medical University
Research purpose	
Main research purpose: To confirm that stellate ganglion block can improve motor symptoms in patients with Parkinson's disease.
 
Secondary research objectives: To determine the efficacy of stellate ganglion block in improving non-motor symptoms, activities of daily living and medication dosage in patients with primary Parkinson's disease.

Research hypothesis	Stellate ganglion block can improve motor and non-motor symptoms in patients with primary Parkinson's disease.
Study design	Single-center, randomized, open-label
Sample size	This study was a randomized controlled trial. The experimental group was treated with standard Parkinson's disease treatment + stellate ganglion block (SGB), and the control group was treated with standard Parkinson's disease treatment. According to the literature review and previous clinical observations, the standard deviation of the MDS-UPDRS scale score in the control group was 9.58 points, and the MDS-UPDRS-III score in the experimental group was expected to decrease by 10 points. 80%, and the loss to follow-up rate was 20%. According to the formula for calculating the sample size, 19 subjects were required to be studied in each of the experimental group and the control group, and at least 38 subjects were included in total.
Research object	
Diagnostic criteria: Parkinson's disease patients who met the 2016 MDS criteria for "probable PD" or "diagnosed PD"
 
Inclusion criteria:
 
 1. Age 45-80 years old; 2. Patients with Parkinson's disease who meet the diagnostic criteria of "probable PD" or "diagnosed PD" in MDS in 2016; 3. The patients or their legal guardians agree to participate in this trial and sign the informed consent form; 4. Hoehn-Yahr (H&Y) level 3 to 5; 
Exclusion criteria:

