	
 1. Those who are allergic to local anesthetics; 2. Those who are unable to cooperate with sports or non-motor function monitoring; 3. Exclude patients with Parkinson's superimposed syndromes, such as corticobasal degeneration, dementia with Lewy bodies, multiple system atrophy, progressive supranuclear palsy; and secondary Parkinson's syndromes, such as vascular parkinsonism, drug poisons or patients with Parkinson's syndrome caused by trauma; 4. Refuse to sign the consent form.

Key Interventions
	
Experimental group: standard treatment of Parkinson's disease + SGB
 
Control group: standard treatment for Parkinson's disease

Follow-up
	
Intervention follow-up period: On Day0, Day5 and Day10 of the first, second and third cycles, the visiting schedule was used to record the required information. The interval of each cycle was 1 month, and the total follow-up time was 3 months.
 
Follow-up period: Modified MDS-UPDRS (Revised Movement Disorders Association Unified Parkinson's Disease Rating Scale) III scores were collected every month after treatment.

Evaluation index
	
Primary end point: MDS-UPDRS score.
 
Secondary end points: NMSS (Parkinson's disease Non-motor Symptom Evaluation Scale), PDQ-39 (39-item Parkinson's disease questionnaire), 10M-WT (walking speed test), H&Y grading (Hoehn Yahr (modified) Parkinson's disease grading), LDE (dopa equivalent dose).

Statistical method
	
SPSS25.0 software was used to analyze the data, and the measurement data were expressed by mean and standard deviation ($\bar{X} \pm S$). For those with normal distribution and homogeneity of variance, paired sample T test was used for intra-group comparison, two independent samples T test was used for inter-group comparison, and t 'test was used for those with uneven variance. The count data were expressed as percentage (%), and the chi-square test was used to compare the total effective rate between groups. $P < 0.05$ was considered as statistically significant difference.

Study time
	
Expected enrollment time of the first subject: 2022-01-01
 
Expected enrollment time of the last subject: 2022-06-30
 
Expected end time: 2024-06-30

Visit Schedule

	Screening stage	Intervention follow-up period			Observational follow-up period	Exit supervision
		Into the group	Follow-up 1	Follow-up 2	Follow-up 3	

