B protein, IL-1 β and TNF- α , and CGRP through the neuro-endocrine-immune system; and It has neuroendocrine regulating effect: can regulate calcitonin, NO, endothelin, serum adrenocorticotrophic hormone (ACTH), α -melanocyte stimulating hormone (MSH) and β -endorphin (β measurement end), etc^[19]; Parkinson's patients have neuro-endocrine-immune system dysfunction. When we used SGB to treat dizziness in PD patients in our previous clinical practice, we unexpectedly found that SGB significantly improved the patients' motor and non-motor symptoms.

At present, there are no reports on the application of SGB in the treatment of Parkinson's patients at home and abroad. Based on the previous clinical observation, this topic intends to use SGB to treat patients with advanced Parkinson's disease through an open, randomized controlled small-sample clinical study, so as to clarify the ability of SGB to treat patients with Parkinson's disease. Effectively improve motor symptoms and non-motor symptoms in patients with advanced Parkinson's disease.

2. Research purpose

Main research purpose: To confirm that stellate ganglion block can improve motor symptoms in patients with Parkinson's disease.

Secondary research objectives: To determine the efficacy of stellate ganglion block in improving non-motor symptoms, activities of daily living and medication dosage in patients with primary Parkinson's disease.

3. Research hypothesis

Stellate ganglion block can improve motor and non-motor symptoms in patients with Parkinson's disease.

4. Study Design

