4.3 Sample size calculation

This clinical trial adopts the sample size calculation formula of 2 groups of quantitative data.

$$n = \frac{(Z_{\alpha} + Z_{\beta})^2 * 2\sigma^2}{\delta^2}$$

Calculation formula:

n represents the sample size of each group.

Take α as 0.05, Z value as two-sided, $Z_{\alpha} = 1.96$; β as one-sided, take power (test power) as 0.8, $Z_{\beta} = 0.84$.

σ represents the difference between the standard deviations of the treatment group and the control group, which is about 9.58 according to previous observations; δ represents the difference of the mean, that is, the difference between the mean of the treatment group and the control group, which is 10; the loss to follow-up rate is 20%.

According to the formula for calculating the sample size, there were 19 subjects in each of the experimental group and the control group, and a total of 38 subjects were included.

5. Subject recruitment

A total of 38 middle-advanced primary PD patients and controls who met the requirements in the inpatient or outpatient department of neurology of Zhujiang Hospital were continuously recruited.

6. Research subjects

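### The main objective is motor, but the primary endpoint is an MDS-UPDRS score not limited to Part III, and the SD of 9.58 is not tied to Part III

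*Protocol*

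**What the plan says.** **Objectives (synopsis and section 2).** The main one is motor: "Main research purpose: To confirm that stellate ganglion block can improve motor symptoms in patients with" Parkinson's disease. The others are ranked below it: "Secondary research objectives: To determine the efficacy of stellate ganglion block in improving non-motor symptoms, activities of daily living and medication dosage".

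**Primary endpoint.** The synopsis has "Primary end point: MDS-UPDRS score". Sections 10.1 and 13.2.6 name the modified MDS-UPDRS, again with no part specified, and the visit schedule lists only MDS-UPDRS as the main indicator. Section 10.1 describes the instrument as one "which has four main parts, including both physician and patient aspects, the first part is psychological, behavioral and emotional", then lists daily living, motor symptoms and complications as parts two to four.

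**Where Part III is named.** The synopsis follow-up row says that "III scores were collected every month after treatment", and the synopsis gives the expected effect on that part: "and the MDS-UPDRS-III score in the experimental group was expected to decrease by 10 points".

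**Sample-size inputs.** Just before that effect, the synopsis says "the standard deviation of the MDS-UPDRS scale score in the control group was 9.58 points". Section 4.3 names no score for either input. It says "σ represents the difference between the standard deviations of the treatment group and the control group, which is about 9.58 according to previous observations" and defines δ as a between-arm difference in means of 10.

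**The concern.** The objective, the endpoint and the sample-size inputs should all refer to one score, and here they do not. The objective and the synopsis effect point to Part III. The endpoint statements point to the MDS-UPDRS without restriction, and section 10.1 spells out all four parts. The protocol writes III in some places, so its absence from every statement of the primary endpoint cannot safely be read as shorthand.

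Two things are at stake:

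- **The meaning of a positive result.** A test on a four-part score mixes in mood and behaviour, daily living and complications. A significant difference could come from those parts and would not confirm a motor benefit. The wording also lets an analyst test either the whole scale or Part III and call it prespecified. In an open-label trial (section 4.2) that freedom weakens the claim further.
- **The power.** The 80% figure holds only for a score with a between-arm difference of 10 and a within-arm SD of about 9.58. The protocol does not say which score has both properties.

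**Working it through.** **Inputs (section 4.3 and synopsis).** Two-sided α = 0.05 (Z = 1.96), power 0.80 (Z = 0.84), δ = 10, σ = 9.58, loss to follow-up 20%, allocation 1:1 (section 4.2).

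**The protocol's own figure.**

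n = (1.96 + 0.84)² × 2σ² / δ² = 7.84 × 2 × 91.7764 / 100 = 14.39, so 15 evaluable per arm.

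15 / (1 − 0.20) = 18.75, so 19 per arm and 38 in total. This matches the protocol.

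The planned analysis is a t-test. With 15 per arm, the noncentral t distribution (28 degrees of freedom, noncentrality δ / (σ√(2/15))) gives power 0.788 at 10/9.58. A standardised difference of 1.06 is needed for 80%; the plan has 10/9.58 = 1.04.

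**What the formula requires.** The term 2σ² needs a common within-arm SD. Section 4.3 words σ as a difference between two SDs, which the formula cannot use. It needs δ as a between-arm difference. Section 4.3 says so, but the synopsis words the 10 points as a fall in the experimental group.

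**If the endpoint is the four-part score.** The protocol gives neither a difference nor an SD for it. All inputs in this table are therefore assumptions; power is for 15 evaluable per arm, two-sided 0.05.

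| Assumed difference | Assumed SD | Power |
|---|---|---|
| 10 | 20 | 26% |
| 10 | 15 | 42% |
| 15 | 20 | 51% |
| 15 | 15 | 75% |
| 15 | 12 | 91% |
| 20 | 15 | 94% |

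**If the endpoint is Part III, δ = 10, but its SD is not 9.58.** The SDs are assumed; the formula is the protocol's, with 20% loss.

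| Assumed Part III SD | Evaluable per arm | Enrolled per arm (plan: 19) |
|---|---|---|
| 8 | 11 | 14 |
| 11 | 19 | 24 |
| 12 | 23 | 29 |
| 15 | 36 | 45 |

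For example, at SD 12: 7.84 × 2 × 144 / 100 = 22.58, so 23; 23 / 0.8 = 28.75, so 29.

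**The case against.** The best defence is that Part III is plainly what was meant. The four-part text in section 10.1 is a parenthesis describing the instrument, and nowhere is the endpoint defined as a total. The SD and the Part III effect stand side by side as inputs to one formula, so the natural reading is one score with its label shortened the first time. The document reads as a rough translation; the wording of σ cannot be literal, since the formula uses 9.58 as a common SD and returns 19. A second line of defence is that the research hypothesis covers motor and non-motor symptoms alike, which a whole-scale score would suit.

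Much of this is fair. Nothing in the protocol shows that 9.58 is wrong for Part III. The σ and δ wording changes no number. The assumed inputs run in both directions, so they show that power depends on the score, not that the trial is underpowered. The defect is an unspecified score, not a prescribed four-part test.

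The defence does not settle the matter, however. Its two lines point to different scores, which is exactly the ambiguity. The broader hypothesis leaves the main objective motor. A statistical analysis plan, which is not at hand, could only choose between conflicting statements; naming the primary score is the protocol's task.

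**Conclusion.** The concern holds and needs correcting. All three statements of the primary endpoint leave the score unrestricted, while the main objective and the synopsis effect are motor. Followed as written, the primary test can be run on a score that includes domains the protocol ranks as secondary, and it may then fail to answer the main question.

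The sample size of 19 per arm is not shown to be wrong: it follows from 10 and 9.58. What is missing is the link between those figures and one named score. If both are Part III values, 19 per arm stands, with t-test power of 79% at 15 evaluable. If 9.58 is not a Part III SD, or the four-part score is intended, the power is unknown from the protocol. The figures for those cases rest on assumed differences and SDs and show sensitivity only.

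Confidence is high on the endpoint mismatch. Whether 9.58 is a Part III SD cannot be determined from the protocol.

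**What to change.** 1. In the synopsis, 10.1 and 13.2.6, name MDS-UPDRS Part III as the primary endpoint. Report the whole-scale score and Parts I, II and IV, if wanted, as secondary.
2. In 4.3, define σ as the common within-arm SD of Part III and δ as the between-arm difference in Part III. Make the synopsis sample-size text agree.
3. Before relabelling, check the source of 9.58. If it is not a Part III SD, recalculate the sample size from one that is, or restate the power at 15 evaluable per arm.
4. If the sponsor prefers the four-part score as primary, reword the main objective to match and base the sample size on that score's own difference and SD.

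**Cost.** If 9.58 is confirmed for Part III, the change is wording only, since Part III is already collected. Otherwise the sample size or the quoted power changes, possibly for the worse. With Part III named, the whole-scale score loses its primary status.

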Supervision stage	V _S	V ₁	V ₂	V ₃	V ₄	
Supervision time	-1day	0	4weeks ±3	8weeks ±3	12weeks±3	
Informed consent	*					
Main evaluation indicators (MDS-UPDRS)	*		*	*	*	when necessary
Secondary evaluation indicators (NMSS、PDQ-39、10M-WT、H&Y、LDE)	*		*	*	*	when necessary
Demographic information^A	*					
Medical history^B	*					
Vital signs^C	*		*	*	*	*
Physical examination^D	*		*	*	*	*

Laboratory tests (hematology/biochemistry/urinalysis)^E	*		*	*	*	必要时
Blood biomarkers^F	*				*	
Film degree exam^G	*				*	
Previous/concomitant medications^H	*					
Adverse event	*	*	*	*	*	*

Remark:

A. Demographics will include the subject's date of birth, gender, ethnicity, education, marriage, occupational information;

B. Medical history includes comorbid diseases and other clinically significant past medical history, medication history, and surgical trauma history;

C. Vital signs will include blood pressure, pulse rate, respiration and temperature;

D. Physical examination includes medical physical examination and neurology specialist physical examination;

E. Clinical laboratory examination: blood routine, serum biochemistry, coagulation, ceruloplasmin, gene expression level;

F. Blood biomarkers: IL-2, APEO, α -synuclein, DJ-1 protein, etc.;

G. Imaging examination: MRA, SWI;

H. The type, dose, and time of previously used drugs.

1. Research background

Parkinson's disease (PD) is a relatively common degenerative disease of the central nervous system, and China's population has grown significantly over the past few decades, resulting in a rapid increase in the number of elderly people; 2016 Global Burden of Disease Study Report It is said that the number of PD patients in China accounts for about 23% of the total PD population in the world^[1]; by the end of 2020, it is estimated that the number of people with Parkinson's in China will be about 3.62 million, and it is estimated that by 2030, 50% of PD patients in the world will be Chinese^[2]. Parkinson's disease is mainly manifested by motor symptoms such as bradykinesia, rigidity, and tremor, as well as non-motor symptoms such as autonomic dysfunction, sleep disturbance, and hyposmia^[1].

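### No deciding occasion is named for the primary MDS-UPDRS comparison, although the score is scheduled at many occasions, tested at an unadjusted P<0.05 and sized as a single comparison

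*Protocol*

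**What the plan says.** Only the protocol is available. On when the primary score is measured, it says four things:

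- **Section 10.1** (primary endpoint): "The first, second, and third cycles of Day0, Day5, and the last day were measured and recorded". The same section says that "each cycle is carried out for 6-10 days, and the interval between each cycle is 20 ± 7 days".
- **Synopsis, follow-up row**: information is recorded "On Day0, Day5 and Day10 of the first, second and third cycles", without limiting this to one arm. In a later follow-up period, Part "III scores were collected every month after treatment".
- **Visit table and section 8.3**: MDS-UPDRS is collected at screening and then at three visits, "Treatment stage: V2 4 weeks, V3 8 weeks, V4 12 weeks". The table has no Day 5 or last-day visit.
- **Section 7.2**: each cycle has 10 daily blocks, "with a 20-day interval between the two cycles". This differs from the ranges in 10.1.

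On the test, sections 13.2.2 and 13.2.6 give a two-sided level of 0.05, an independent-samples t-test between arms and a paired t-test within arms. They name no occasion and no summary over time, do not say whether the final value or the change is compared, and do not rank the between-arm test above the within-arm test.

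Section 4.3 sizes one between-arm difference of 10 points with SD 9.58, two-sided alpha 0.05, power 0.8 and 20% loss. The synopsis attaches the 10 points to Part III and the SD to the MDS-UPDRS score without naming a part. Neither figure is tied to an occasion.

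**The concern.** The main objective in section 2 is to confirm a motor benefit, and section 4.2 makes the trial open to both investigators and patients. A confirmatory claim needs one comparison fixed before the data are seen. Here the endpoint, its readings, the test and the threshold are all fixed, but the choice that turns them into one test is left open. Whoever analyses the data could report cycle 1 Day 5, the end of cycle 3, week 12 or another occasion as the primary result and remain within the text.

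Two things are at stake. First, the 5% error level holds only if the occasion is chosen without sight of the results. Second, one of the candidates, the last day of a cycle, is defined by block treatment that control patients do not receive. If it were chosen, the arms need not be compared at the same time from randomisation.

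**Working it through.** **1. The plan's own sample size.** Inputs from section 4.3: Z values 1.96 and 0.84, SD 9.58, difference 10, loss 20%.

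n = (1.96 + 0.84)² × 2 × 9.58² / 10² = 7.84 × 183.55 / 100 = 14.4, so 15 per arm. With loss: 15 / 0.8 = 18.75, so 19 per arm and 38 in total.

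The stated figure is reproduced, and it corresponds to one test at two-sided 0.05. By the noncentral t distribution, 15 per arm give a power of 0.788.

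**2. Count of occasions.**
- Section 10.1: 3 cycles × 3 days = 9 readings. Cycle 1 Day 0 is baseline, which leaves 8.
- Visit table and 8.3: 3 post-baseline visits.
- Synopsis: monthly Part III scores, number not given.

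**3. False-positive chance if every occasion is tested and any one may be reported.** Trials with no true effect were simulated (40,000 per case), with a two-sided t-test at 0.05 at each occasion and equal correlation r between occasions. The correlation is an assumption. The table shows 19 per arm; results with 15 per arm are within about half a percentage point.

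| Occasions | r = 0.9 | r = 0.8 | r = 0.5 |
|---|---|---|---|
| 1 | 5% | 5% | 5% |
| 3 | 8.5% | 10% | 12.5% |
| 8 | 12% | 16% | 25% |

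False results in favour of the block are about half of these: roughly 4-6% for 3 occasions and 6-13% for 8, against 2.5% for one test.

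**4. When the last day of cycle 3 falls**, counting cycle days plus gaps:
- shortest in 10.1: 3 × 6 + 2 × 13 = Day 44
- nominal in 7.2: 3 × 10 + 2 × 20 = Day 70
- longest in 10.1: 3 × 10 + 2 × 27 = Day 84

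Each is one day less if the first block day counts as Day 0. Section 10.1 does not say which day serves as the last day for a control patient.

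**5. Time since the last block at week 12 (Day 84):** 84 − 44 = 40 days, 84 − 70 = 14 days and 84 − 84 = 0 days for the same three cases.

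**6. How far the 79% depends on the chosen score and occasion.** Illustrations with 15 per arm: about 60% power if the difference is 8 with SD 9.58, and about 60% if the difference is 10 with SD 12.

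**The case against.** The strongest reply is that no section says each occasion will be tested or that success at any one is enough. Section 4.3 sizes a single comparison, which suggests that one was intended, and a statistical analysis plan might name it. The first part is right. A reader might infer that this trial has a false-positive rate of up to 25%; the documents do not support that. The percentages describe what the open wording permits under an assumed correlation, not a stated procedure. The possibility of a separate plan does not remove the point, because the protocol itself defines the endpoint, the readings, the test and the threshold, and its own assessment schedules are not reconciled.

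Four other stronger readings also fail:

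- **That the schedules exclude each other.** Cycle-day readings, four-weekly visits and later monthly scores may be meant to add up. They are unreconciled, not proven incompatible.
- **That the arms will be compared at different times.** This arises only if the last day is chosen. Weeks 4, 8 and 12 are common to both arms, and the synopsis gives Days 0, 5 and 10 without naming an arm.
- **That 38 patients are too few because of multiplicity.** The size is right for one named test.
- **That section 10.2 shows a deliberate difference.** Its wording for the secondary scales names only the last cycle ("On Day0, Day5, and the last day of the third cycle, the scale data were measured and recorded"), but the visit table and 8.3 also collect those scales at weeks 4, 8 and 12. Little should rest on that contrast in a translated text.

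**Conclusion.** The point holds. The primary comparison is not defined in advance: the score is listed at eight post-baseline cycle days and three visits, with further monthly Part III scores, and no occasion is designated as deciding. This conflicts with a sample size built for one between-arm test at 5%.

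The possible inflation is to about 9-13% with three occasions and 12-25% with eight. It is conditional on testing all of them and being free to report any one, with equal correlation of 0.9 to 0.5 assumed. The fault does not depend on those figures: even without deliberate selection, the answer to the main question could turn on the day chosen. The variable timing of the last day, about Day 44 to Day 84 for cycle 3, is a further reason not to leave the choice open.

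**What to change.** In sections 10.1 and 13.2.6, name one between-arm comparison: one stated score (Part III or total), as final value or change from baseline, at one occasion set by the same calendar rule from randomisation in both arms, tested once at two-sided 0.05. Label all other occasions and the within-arm paired tests as secondary or descriptive.

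Reconcile the assessment times in the synopsis, the visit table, 8.3 and 10.1. Reconcile the cycle length and gap in 7.2 and 10.1 as well; which schedule is right is a clinical matter and is not decided here.

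Week 12 (V4) is one candidate, since both arms attend it, but the sponsor should weigh two points. The visit table, which is broken in the available text, may place V4 under observational follow-up, while 8.3 calls it treatment stage. Time since the last block would also vary within the experimental arm, from 0 to about 40 days on the 10.1 ranges. Another occasion may be justified.

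**Cost.** The change is one of wording and keeps 38 patients. A benefit seen only at another occasion could no longer be claimed as the primary result. The sponsor must also justify the 10-point difference and the SD of 9.58 for the chosen score and occasion; without that, the power of about 79% with 15 per arm is not assured.

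The alternative, letting any occasion carry the claim with a Bonferroni correction, costs more by the 4.3 formula. With three occasions (alpha 0.05 / 3 = 0.0167) it needs 20 per arm, 20 / 0.8 = 25 with loss, 50 in total. With eight (0.05 / 8 = 0.00625) it needs 24 per arm, 24 / 0.8 = 30 with loss, 60 in total.
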